Across populations, regular exercise improves physical function and reduces fatigue. Most of these studies incorporate continuous moderate-intensity exercise (CME), where aerobic exercise is performed at 70%-75% of maximal heart rate (HRmax) continuously for a specified duration (i.e., a 30-min walk). We found that CME + moderate-intensity resistance exercise improves physical function in older PWH, with additional improvements from a higher-intensity continuous aerobic + resistance exercise program^23. Further, only our higher-intensity (i.e., 80-90% HRmax) continuous aerobic + resistance intervention improved fatigue. Lastly, despite improvements in physical function and fatigue during the 6-month intervention, less than 50% of our participants continued to exercise at least once a week following the supervised intervention, demonstrating that even when exercise is beneficial it can be difficult for PWH to maintain. These data are promising, but suggest that an **innovative approach to exercise is needed to improve physical function, reduce fatigue, and maintain a self-directed exercise habit among older PWH**. Further, generalizability is limited by a small sample size, few women, and lack of different exercise types, leaving important knowledge gaps.

High-intensity interval training (HIIT) uses repeated alternating short bouts of high-intensity (e.g., 80%-95% HRmax) and lower intensity aerobic exercise (e.g., 60% HRmax). HIIT is safe and has superior efficacy in improving health outcomes compared to CME in those with chronic illness (e.g., coronary artery disease, diabetes), yet **little is known about HIIT for PWH**. HIIT also reduces body fat, improves muscle mass, and enhances mitochondrial bioenergetics (i.e., mitochondrial respiration rate and electron transport chain [ETC] activity), mechanisms proposed to underlie reductions in fatigue. At both sites (University of Colorado Denver and University of Washington), participants are undergoing an optional sleep sub-study that aims to characterize the effects of two exercise interventions, HIIT and CME, on sleep and inflammation in older PWH.

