**B. Description of Population to be Enrolled:**

|            | Consented | Begin Intervention | Number of women | Complete Intervention |
|------------|-----------|--------------------|-----------------|-----------------------|
| Colorado   | Up to 100 | N=60               | Goal 25%        | N=50                  |
| Seattle/UW | Up to 100 | N=60               | Goal 25%        | N=50                  |
| UAB        | Up to 100 | N=60               | Goal 25%        | N=50                  |

This study will involve the recruitment and retention of men and women ( $n=180$ ) at three sites ( $n=60$  each site) with HIV infection who are stable on HIV antiretroviral therapy. Study volunteers must meet general criteria to be eligible for further screening for participation in the study. In most cases, this information will be acquired during a telephone interview prior to a screening/consent visit. *The inclusion and exclusion criteria have been carefully selected to enroll the most appropriate study population while also protecting the generalizability of the findings.* All participants will engage in a 16-week randomized exercise intervention (high-intensity interval training [HIIT] vs continuous moderate exercise [CME], followed by a 12-week exercise maintenance intervention in which participants are also randomized to a coaching vs control intervention. Up to 40 participants will be given the opportunity to co-enroll in a qualitative substudy (Aim 3) where they will participate in three one-on-one interviews (at weeks 0,16,28) to capture perspectives on sustaining a self-directed exercise habit. Up to 40 participants (Colorado and Washinton only) will be given the opportunity to participate in an MRI/MRS substudy with imaging at baseline and week 16. Up to 20 participants (Colorado, Washinton, and Alabama) will be given the opportunity to complete the 16 week exercise intervention at a recreational center. The total study duration will be 28 weeks at UCD and UW with the option to enroll in a 12 month follow up (48 weeks). The total study duration will be 48 weeks at UAB.

**Characteristics of the Population:** Potential participants will be recruited from HIV specialty clinics at our sites. Adults living with HIV will be included if they meet the following eligibility criteria:

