*Baseline visit #2* will include a fasting blood draw (i.e., complete blood count, metabolic panel, HIV-1 RNA, CD4 count, PBMCs, FSH, and stored sample for future analyses) and vastus lateralis muscle biopsy (this will be optional), both collected between 8-10am. CD4 count does not to be measured if results from clinical care are available within the prior 12 months HIV-1 RNA if available within the prior 3 months and no reason to expect failure of treatment (i.e, stopped ART).. Complete blood count, complete metabolic panel, and thyroid stimulating hormone does not to be measured if results from clinical care is also available within the prior 3 months. The blood draw and the muscle biopsy will be repeated following the 16-week intervention. Blood labs may need to be repeated or redrawn at subsequent screening visits. Specimens of the *vastus lateralis* muscle will be obtained by percutaneous biopsy from fasted participants who have refrained from exercise for  $\geq 48$  hours. After cleansing the thigh with chlorhexidine, 1% lidocaine without epinephrine will be injected subcutaneously. A 3-5 mm incision will be made in the skin and fascia over the belly of the *vastus lateralis*, and 100-150 mg of muscle tissue will be removed using a Bergstrom side-cutting biopsy needle. The incision will be closed using Steri-strips; a compression wrap and ice will be applied for 30 minutes. Participants will be instructed on wound care and will be contacted by study staff 48-72 hours post-procedure to ensure healing. [name] has performed over 80 biopsies and [name] has performed over 50 biopsies with no prior complications and excellent tissue yield (. Following the biopsy, study staff will explain the *Lee Fatigue Scale* (LFS) and use of the accelerometer (see below) to the participant.

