*Baseline visit #3. Physical function and (optional) muscle ultrasound.* The **primary physical function outcome will be 400-MWT**, a well-established measure shown to better discriminate early physical function decline among higher functioning adults, and is a reliable outcome in clinical trials, including the LIFE Trial. The Short Performance Physical Battery (SPPB) and a modified version (mSPPB) will be obtained. The SPPB is an objective assessment of physical function associated with short-term mortality, disability, and hospitalizations. The mSPPB improves discrimination of physical function by increasing repeat chair stands from 5 to 10, standing balance test for 30 seconds instead of 10, and adding a single leg stand. Physical function will be measured every 4 weeks by a research assistant blinded to intervention arm. The 400-MWT, SPPB, and mSPPB will be administered at both sites using standard scripts. Additional measures of frailty will include self-reported fatigue, weight loss, and exhaustion, and objective measures of grip strength by hand held dynamometer. The 400-MWT and the 10x chair stands from the mSPPB will be done every 4 weeks; the full physical function battery will be completed at baseline, week 16, and week 28. For the optional muscle ultrasound, we will collect sonographic images to provide estimates on lean muscle mass (aggregate muscle thickness, cm) and myosteatosis (grayscale values) using the Phillips Lumify L 12-4 linear array transducer. Sonographic estimates of lean muscle mass will be taken at the midpoint of the upper trapezius, pectoralis major, lateral deltoid, brachioradialis, rectus femoris, and tibialis anterior while the participant lays supine for 15-20 minutes.

*Baseline visit #4: MRI/MRS.* Prior to the initiation of exercise training, participants will undergo baseline MRI/MRS studies as detailed below. All of the proposed imaging modalities in the ancillary HEALTH+ Study Aims 1-3 can be completed within one-hour in the research scanner, located in the building adjacent to the Exercise Research Laboratory at UCD-AMC and the 14T MR Lab and [name] laboratory facilities at UW. Participants will be instructed to avoid vigorous activity for 2 days prior to the imaging studies. The imaging will be repeated during weeks 16, or within 4 weeks of the final exercise visit for PWH in the HEALTH study.

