**Intervention:** Participants will complete 16 weeks of supervised CME or HIIT 3 days/week in the University of Colorado-Denver Exercise Research Laboratory, at the Prevention Center at Fred Hutch (University of Washington (UW) site, and at the Center of Exercise Medicine at University of Alabama. Participants will be given the option to complete 16 weeks of exercise at a recreational center if travel to the University of Colorado-Denver, University of Washinton, and University of Alabama at Birmingham is difficult. The recreation center must meet certain requirements (see risk section). Our study staff will visit the site in advance to ensure appropriate equipment is available. Any fees for membership will be covered by the study team (paid directly to the recreation center, not to the participant). Weeks 1-2 will focus on familiarization with the exercises at low intensity. These sessions will still occur at the University of Colorado-Denver center even if a participant choses to exercise at a local recreation center for the remainder of the 16 weeks. The intensity and duration of exercise will be progressed over the first 3-8 weeks to reach the individualized goals. The HIIT and CME interventions will be matched for exercise volume using standard equations for estimating caloric expenditure assuming 5 kcal/L O2 and 50 min/session duration for CME to meet the PA guidelines (Table 4). The total exercise time will differ by 8 minutes, but HIIT includes rest intervals and variety, which prior studies have shown is associated with greater enjoyment and physiologic benefits than CME.

**HIIT.** Following a 5-minute warm-up at 50% HRR (Heart rate reserve), high and moderate-intensity exercise bouts will alternate: Five bouts of 4-minute high-intensity exercise (90% HRR) will alternate with four 3-minute bouts of moderate-intensity exercise (50% HRR). The total exercise time will be 42 minutes.

**CME.** Following a 4 minute warm-up at 50%  $\text{VO}_{2\text{peak}}$ , the participant will walk for 50 continuous minutes at 60% HRR^140.

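### The MRI/MRS pre-scan rule bars only undefined vigorous activity for 2 days, so for scans close to training the time since the last aerobic bout can differ between HIIT and CME

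*Combined protocol and SAP*

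**What the plan says.** **Imaging.** Section IV.C, Baseline visit #4, gives one preparation rule: "Participants will be instructed to avoid vigorous activity for 2 days prior to the imaging studies". The same paragraph sets the follow-up timing: "The imaging will be repeated during weeks 16, or within 4 weeks of the final exercise visit for PWH in the HEALTH study". It gives no lower limit on time since the last session.

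**Training.** Both arms train 3 days a week (Section IV.C, Intervention). In CME "the participant will walk for 50 continuous minutes at 60% HRR". HIIT has five 4-minute bouts at 90% HRR, which the protocol calls high-intensity. The opening aims pages and Section IV.B name CME as moderate. The Background, citing the national activity guidelines, treats moderate and vigorous as separate categories. Resistance exercise, common to both arms, progresses to what the protocol calls moderate intensity (70–80% 1-RM).

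**Biopsy, for comparison.** Under Baseline visit #2, specimens are "obtained by percutaneous biopsy from fasted participants who have refrained from exercise for" at least 48 hours, with no intensity qualifier. Table 3 also places the follow-up biopsy at least 48 hours after VO2 testing, and Section IV.D asks participants to return for it within 10 days of the final session. The MRI row of Table 3 carries no such note.

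**Role of the contrast.** The sample-size section calls the muscle substudy exploratory. The MRI/MRS analysis paragraph makes change from baseline primary and the HIIT-versus-CME comparison secondary.

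**The concern.** A rule for preparing participants before an outcome measurement should act alike in both randomised arms. This one is worded by exercise intensity, which is the factor being randomised. On the natural reading, a HIIT session is ruled out in the 2 days before a scan and a CME session is not. At baseline this does little harm, because participants are sedentary and training has not begun. It matters at the repeat scan.

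If recent exercise shifts the imaging outcomes, unequal rest would enter the arm difference as though it were a training effect. The hypotheses most exposed are 2A (oxidative function by 31P-MRS) and 3A (vascular and metabolic response by vPIVOT), both of which predict a larger gain with HIIT. Hypothesis 2B relates the MRS change to skeletal-muscle mitochondrial measures. That link is also looser than it need be, because the biopsy follows a full abstention from exercise and the scan need not.

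**Working it through.** The plan states no figure on this point to reproduce. The check asks how many CME scans the rule could leave less than 2 days after an aerobic session, and how large an acute effect would have to be to matter.

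**1. Share of CME scans affected.** HIIT is taken as 0 for aerobic bouts if the rule is followed literally.

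- *All scans during training, sessions Monday/Wednesday/Friday, scan on a random day of the week (assumed).* If the scan precedes any session that day, Tuesday, Thursday and Saturday are under 2 days from a session: 3/7 = 43%. If the scan follows that day's session, every day but Sunday is: 6/7 = 86%.
- *Scans spread evenly over 0–28 days after the final session (assumed).* 2/28 = 7%.

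**2. Days since the last aerobic session.** For scans during training, Monday to Friday, with no session on the scan day:

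| Scan day | CME | HIIT |
|---|---|---|
| Mon | 3 | 3 |
| Tue | 1 | 4 |
| Wed | 2 | 2 |
| Thu | 1 | 3 |
| Fri | 2 | 2 |
| Mean | 9/5 = 1.8 | 14/5 = 2.8 |

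For scans spread over 0–28 days, the mean arm difference is about 0.07 day if HIIT scans due inside 2 days simply move to day 2. It is 1 day if HIIT scans are uniform over 2–28 days (mean 15 against 14). So the average arm difference runs from near 0 to about 1 day, against a permitted spread of 28 days in both arms.

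**3. Acute shift needed for a material bias.** Bias in the arm contrast = share affected × acute shift. As yardsticks I use the between-arm detectable differences in the sample-size section with 12 per group: 0.056 for OxPhos and 30% for the VO2 response. Their SDs are not given. Shift needed for a bias of half the yardstick (0.028, or 15 percentage points):

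| Share of CME scans | OxPhos | VO2 response |
|---|---|---|
| 6/7 | 0.028/0.857 = 0.033 | 15/0.857 = 17.5% |
| 3/7 | 0.028/0.429 = 0.065 | 15/0.429 = 35% |
| 2/28 | 0.028/0.0714 = 0.39 | 15/0.0714 = 210% |

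The last row needs an OxPhos shift 7 times the stated detectable difference (0.39/0.056).

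**4. Effect on error rates.** This uses a two-sided t-test with 12 per group at 0.05 (the level stated for the parent Aims 1 and 2, assumed here) and 80% power, which gives a detectable standardised difference of 1.197. An artefact of 10%, 25% or 50% of that difference would give a false-positive rate of 5.9%, 10.8% or 28.9%. These are illustrations. The documents contain no estimate of the artefact.

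**The case against.** A reader might infer that the rule rests the HIIT arm, lets the CME arm train up to the scan, and so makes time since last bout differ by arm. The documents do not support that as fact. The rule names no arm, *vigorous* is undefined, supervising staff could read it more broadly, and nothing tells CME participants to train before a scan. The sentence also sits in the baseline-visit paragraph, so its use at the repeat scan is implied, not stated. Nor does the rule make HIIT participants skip all training, since resistance work is not barred. All of this stands, and it limits the point to what the rule permits.

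The high shares in the working assume that every scan falls while training continues. The 4-week window allows much later scans. Table 3, as extracted, appears to place the follow-up MRI with the end-of-part-1 procedures, although its header is broken and says these visits can overlap with week 16. That stands too, which is why the range must start at 7%.

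No acute effect of a 60% HRR walk on any imaging outcome is documented. A reader might also extend the worry to hypothesis 1A through intramyocellular lipid, but 1A's approach rests on fat fraction by MRI and muscle ultrasound, and nothing in the documents suggests that recent walking moves these.

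Two things survive. Scans during week 16 are expressly allowed. And if the rule does not carry over to the repeat scan, follow-up imaging has no rest rule at all, which calls for the same remedy.

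**Conclusion.** The point holds in a limited form, and it is minor. The imaging rule is undefined, looser than the biopsy rule, and worded so that it can act differently by randomised arm for scans during week 16 or within 2 days of the final session. Depending on when scans are booked, about 7% to 86% of CME scans could be affected. The range rests on the assumed session pattern and scan dates, and on a literal reading of *vigorous*. For later scans the rule creates no arm difference; what remains is an unstandardised interval of up to 28 days in both arms. Bias in the HIIT-versus-CME imaging contrasts is possible, of unknown size and direction. Only secondary contrasts of an exploratory substudy, and comparability with the biopsy measures, are at stake. The primary 400-m walk analysis is untouched.

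**What to change.** 1. Reconcile the pre-scan rule under Baseline visit #4 with the biopsy preparation under Baseline visit #2, in Table 3 and in Section IV.D. One arm-neutral pre-measurement rest condition should apply to imaging in both arms and at both time points. The biopsy's existing condition of no exercise for at least 48 hours is one already in the protocol. State explicitly that it applies to the repeat scan.
2. Take the date of the last session before each scan from the session logs already kept (Section IV.C, Supervised exercise sessions and Intervention fidelity). These dates are probably available for completed scans as well.
3. Report time since last session by arm.
4. Add a sensitivity analysis of the arm contrast limited to scans at least 48 hours after the last session. It selects on a post-randomisation timing variable and shrinks an already small sample, so treat it as supportive.

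The cost is a sentence or two in the protocol and participant instructions, one derived variable, and scheduling some scans around training sessions.
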